1. STUDY OBJECTIVES

Study aims are to test the efficacy of a mindfulness-based text messaging program for smoking cessation ("iQuit Mindfully"), both as a standalone intervention and in combination with in-person counseling, and examine underlying mechanisms of mindfulness treatment. Approximately 485 participants (maximum 500) will be randomized to one of four groups:

- Usual Care (self-help materials + nicotine patch treatment)
- MBAT (8 weekly virtual MBAT sessions + self-help materials + nicotine patch treatment)
- iQuit Mindfully (iQuit Mindfully text messages + self-help materials + nicotine patch treatment)
- MBAT + iQuit Mindfully (8 weekly virtual MBAT sessions + iQuit Mindfully text messages + self-help materials + nicotine patch treatment)

All study participants will receive self-help smoking cessation materials, including the "Clearing the Air" booklet developed by the National Cancer Institute (NCI) and a referral to the Tobacco Cessation Quitline ([name]). All study participants will also receive nicotine patches. Assessments will occur at baseline and weeks 1, 3, 5, 8, 12, and 24. Primary outcomes are smoking abstinence at 8 weeks after the start of treatment (7-day abstinence, biochemically verified by expired carbon monoxide <6 ppm), 12 weeks after the start of treatment (3 month follow-up; 7-day abstinence, biochemically verified by expired carbon monoxide <6 ppm), and 24 weeks after the start of treatment (6-month follow-up; 7-day abstinence, biochemically verified by saliva cotinine < 20 ng/ml). Secondary outcomes include frequency of home mindfulness practice and self-reported levels of mindfulness, emotions, craving, withdrawal, dependence, self-efficacy, and social support. Aims and hypotheses are outlined below:

Aim I. Test the efficacy of a mindfulness-based text messaging program for smoking cessation ("iQuit Mindfully"), both as a standalone intervention and in combination with in-person counseling.

We hypothesize that:

- 1a) MBAT + iQuit Mindfully will result in higher rates of smoking cessation and lapse recovery than MBAT, which will produce higher cessation and lapse recovery than UC. iQuit Mindfully as a standalone intervention will also produce higher cessation and lapse recovery than UC.
- 1b) As an exploratory aim, we will examine whether poverty status moderates treatment efficacy (i.e., poverty status will predict worse cessation outcomes in MBAT but not MBAT + iQuit Mindfully).

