Power and Sample Size Determination. Sample size was estimated based on the number of participants needed to detect meaningful treatment effects of the iQuit Mindfully and MBAT interventions. We obtained effect sizes (converted to Cohen's *d* for comparability across measures) from relevant meta-analyses and used the Optimal Design program to estimate sample size for GzLMM models. Samoking abstinence in MBIs vs. UC was quantified as *d*=0.35 in a meta-analysis, and a Cochrane review of primarily text messaging-based interventions for smoking cessation concluded an effect size of *d*=0.33. Assuming 80% power, level of significance of .05, two-tailed statistical tests, error variance of 1.0, coefficient variance of 2.0, and oversampling to account for 20% attrition, this results in 145 participants in each treatment group. An unequal allocation ratio was used to allocate fewer participants to usual care (*n*=50), 55,56 for an overall sample size of 485 participants (145 per treatment group and 50 in usual care). We expect this sample size to adequately allow for mediational testing (Aim 2) at the 80% power level. Fritz and MacKinnon for offer a guide regarding sample size required to detect mediated effects and report that 79.9% of studies in their literature review applied mediational testing with less than 400 subjects, suggesting our study plan with 485 subjects will be ample for achieving all study aims.

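### The 145 per group gives 80% power only with equal arms; with usual care cut to 50, the two usual-care contrasts in hypothesis 1a have about 52% after attrition, and no power is stated for them.

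*Combined protocol and SAP*

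**What the plan says.** The power paragraph of section 9 takes two effect sizes from meta-analyses. For the first, "abstinence in MBIs vs. UC was quantified as" d = 0.35; for text messaging the effect is d = 0.33. It assumes 80% power, two-sided 0.05, an error variance of 1.0 and a coefficient variance of 2.0. With "oversampling to account for 20% attrition, this results in 145 participants in each treatment group", the derivation is complete. The next sentence changes the design: "An unequal allocation ratio was used to allocate fewer participants to usual care", namely 50, for a total of 485. No power follows for any comparison against the group of 50.

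On mediation the paragraph says "We expect this sample size to adequately allow for mediational testing (Aim 2) at the 80% power level". The evidence offered is that "79.9% of studies in their literature review applied mediational testing with less than 400 subjects", and the paragraph ends "suggesting our study plan with 485 subjects will be ample for achieving all study aims".

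Hypothesis 1a in section 1 names three contrasts. The first is MBAT + iQuit Mindfully over MBAT. The second is "MBAT, which will produce higher cessation and lapse recovery than UC". The third is that "iQuit Mindfully as a standalone intervention will also produce higher cessation and lapse recovery than UC". Section 9, Aim I, models treatment condition as a fixed effect and tests these through linear contrasts between conditions.

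**The concern.** The precision of a two-group comparison is governed mainly by the smaller group. A per-group size found for equal arms does not keep its power when one arm is cut to about a third. Here the arm that was cut is the comparator for two of the three hypothesis 1a contrasts. It is also the comparator in the d = 0.35 used for planning, so the comparison that this effect describes is one that lost sample size.

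The standalone iQuit Mindfully question is part of the wording of Aim I, and its only named test is against usual care. If that test is null, readers will judge it against a plan that says the sample is sufficient for every aim, when the test may have had roughly an even chance of detecting the effect used for planning.

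**Working it through.** **Inputs.** From section 9: 80% power, two-sided 0.05; d = 0.33 and 0.35; variances 1.0 and 2.0; 20% attrition; 145, 145, 145 and 50 randomised. Total: 3 × 145 + 50 = 485. Completers: 145 × 0.8 = 116 and 50 × 0.8 = 40. The normal approximation is used throughout; 80% power corresponds to a noncentrality of 1.960 + 0.8416 = 2.8016.

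**Reproducing the 145.** The plan gives neither the number of occasions nor the scaling of d, so two readings were tried, both with equal arms and n = 2 × 2.8016² × v / d².

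- Single occasion, v = 1: n = 15.70/0.33² = 144.1 and 15.70/0.35² = 128.1 per arm, before attrition.
- Mean of the three primary visits, with 1.0 and 2.0 read as within- and between-person variance and d on the total SD: v = (2.0 + 1.0/3)/3.0 = 0.778. At d = 0.33, n = 112.1, or 112.1/0.8 = 140.1 with attrition.

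At d = 0.33 the first rounds up to 145 without attrition, and the second comes close to 145 with it. Neither settles which was used, but both assume equal arms. At the planned ratio of 145/50 = 2.9, a single-occasion calculation needs 2.8016² × (1 + 1/2.9)/d² usual-care completers, which is 87 (d = 0.35) or 97 (d = 0.33). The plan yields 40.

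**Power without choosing a d.** Take the plan's premise that 116 against 116 has 80%.

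- 116 against 40: the standard error grows by √[(1/116 + 1/40)/(2/116)] = 1.396. Then 2.8016/1.396 − 1.960 = 0.046, so power is 51.8%.
- 145 against 50, no attrition: the ratio is √[(1/145 + 1/50)/(2/116)] = 1.249, so power is about 61%.
- If the 80% belongs to 145 against 145 instead, 145 against 50 again gives 51.8%, because the allocation ratio is the same.
- Equal arms with the same precision as 116 against 40: 2/(1/116 + 1/40) = 59.5 per arm. The detectable effect is 1.40 times the planned one.

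**Power at the stated d, after attrition.** Power = Φ(d/SE − 1.960); detectable d = 2.8016 × SE.

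| Contrast | Reading | SE | Power at d = 0.33 / 0.35 | Detectable d |
|---|---|---|---|---|
| Arm vs usual care (116 vs 40) | Single occasion | 0.1834 | 43.6% / 48.0% | 0.51 |
| Arm vs usual care (116 vs 40) | Mean of three | 0.1617 | 53.2% / 58.1% | 0.45 |
| MBAT + iQuit Mindfully vs MBAT (116 vs 116) | Single occasion | 0.1313 | 71.0% / 76.0% | 0.37 |
| MBAT + iQuit Mindfully vs MBAT (116 vs 116) | Mean of three | 0.1158 | 81.3% / 85.6% | 0.32 |

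**Binary scale.** The outcome is abstinence, so the calibration was repeated on proportions: 80% at 116 against 116, with usual-care abstinence assumed between 5% and 25% (the plan gives no rate). Power at 116 against 40 is 42–49% with a pooled variance, 55–63% unpooled, and 44–49% for a Wald test on the logit scale.

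**Mediation.** The share of published studies with fewer than 400 subjects describes practice. It contains no path size, comparison or test, so no power figure follows from it. The documents give no path sizes, and no mediation power was calculated here.

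**The case against.** Unequal allocation is legitimate, and the plan discloses and references it. The total is added correctly. These points stand, and none supplies the missing power.

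The plan never says that the 145 assumes equal arms. That is an inference from the order of the sentences and from the readings that come near 145. It is a strong one: no reading tried gives 80% at 145 against 50.

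The analysis set is everyone randomised, with multiple imputation and a mixed model that uses partial follow-up, so counting only completers is somewhat pessimistic. Full retention of information raises the calibrated figure only to about 61%.

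The 51.8% assumes equal outcome variance in the two arms. For a binary outcome the fair statement is a range, 42–63% over the assumed abstinence rates.

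The design is a 2 × 2, and the factorial margins (232 against 156 completers) would have about 89–92% power at d = 0.33–0.35 with unit variance. But hypothesis 1a compares individual conditions, and the model contains treatment condition rather than factorial main effects. Pooling all three mindfulness arms against usual care (348 against 40) reaches only about 60% on the same calibration.

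Hypothesis 1a also covers lapse recovery, which is tested only among participants smoking at the last treatment session. The figures above are for cessation; the lapse-recovery contrasts rest on fewer people.

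On mediation, the plan does cite a sample-size guide, but it reports only the count of study sizes from it.

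**Conclusion.** The concern holds. For cessation, each usual-care contrast in hypothesis 1a has about 52% power after attrition if the 145 delivers 80% with equal arms. Every reading tried lies between 42% and 63%, and none reaches 80%. The 52% rests on the plan's own 80% premise, its own counts and equal variances; it does not depend on d or on the time model. The d-based figures do depend on the two assumed readings.

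MBAT + iQuit Mindfully against MBAT is not affected by the allocation. It has 81–86% on the three-visit reading. On the single-occasion reading it has 71–76%, and 145 is then the size before attrition, so the 20% inflation may not have been applied. Only the program settings can resolve that. The statement that 485 is enough for all aims is wrong for two of the three named contrasts, and the 80% mediation claim has no calculation behind it.

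**What to change.** In the power paragraph of section 9:

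1. For each hypothesis 1a contrast, state power, or the detectable effect at 80% power, at the actual sizes (145 against 50 and 145 against 145), before and after 20% attrition. State the number of occasions, the scaling of d and whether the 145 includes the attrition inflation. On the two readings above, the detectable d against usual care after attrition is about 0.45 to 0.51; the study team's rerun should supply the final value.
2. Remove the statement that 485 suffices for all aims, and say that the usual-care contrasts fall below 80%. Note that lapse recovery uses a smaller subset.
3. Delete the 80% mediation sentence, or replace it with a calculation that gives the assumed path sizes and says whether the comparison is the pooled mindfulness arms or each arm against usual care.

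The cost is one rerun of the power calculation and new wording in one section. Enrolment, allocation and the planned contrasts need not change. The trade-off is a less favourable stated power for the usual-care comparisons.

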Aim II. Investigate the mechanisms through which mindfulness training impacts smoking cessation. Participants will complete questionnaires from baseline through 24 weeks after the start of treatment, in addition to intensive diary assessments for 6 contiguous weeks during treatment. We hypothesize that:

- 2a) Compared to UC, the mindfulness treatment arms (MBAT, iQuit Mindfully, and MBAT + iQuit Mindfully) will increase mindfulness; reduce negative affect (NA) and volatility of NA (i.e., greater affective stability); increase positive affect; reduce craving and withdrawal; and increase self-efficacy and social support, all of which will mediate effects of the mindfulness-based treatment arms vs. UC on abstinence.
- 2b) Compared to UC, MBAT, iQuit Mindfully, and MBAT + iQuit Mindfully will all attenuate links between NA/craving and smoking. That is, in addition to reducing NA and craving (2a), mindfulness training is hypothesized to weaken the relationships between NA/craving and smoking.

2c) Compared to MBAT, MBAT + iQuit Mindfully will produce stronger effects on the above mechanisms (2a, 2b). Mechanisms outlined in 2a will mediate effects of MBAT + iQuit Mindfully vs. MBAT on abstinence.

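### The 80% power stated for Aim II mediation has no calculation behind it, and the total of 485 hides a usual-care arm of 50

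*Combined protocol and SAP*

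**What the plan says.** The power paragraph of Section 9 derives 145 per treatment group from two abstinence effects. For mindfulness-based interventions, "MBIs vs. UC was quantified as *d*=0.35 in a meta-analysis"; the text-messaging review "concluded an effect size of *d*=0.33". The calculation is two-sided at 0.05 with 80% power, and its two variance inputs are 1.0 and 2.0. On dropout the paragraph states: "oversampling to account for 20% attrition, this results in 145 participants in each treatment group". Usual care (UC) is then set at 50 by unequal allocation, for a total of 485.

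For Aim II the paragraph adds "We expect this sample size to adequately allow for mediational testing (Aim 2) at the 80% power level". It mentions a published guide to sample size for mediated effects but takes no required sample size from it. What it reports is that "79.9% of studies in their literature review applied mediational testing with less than 400 subjects", and it concludes that 485 is enough for every aim.

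Section 1 (Aim II) sets out what has to be powered. Hypothesis 2a lists eight mechanisms, "all of which will mediate effects of the mindfulness-based treatment arms vs. UC on abstinence". Hypothesis 2b also compares with UC. Hypothesis 2c compares MBAT + iQuit Mindfully with MBAT and does not involve UC.

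**The concern.** How many subjects other investigators enrolled describes practice. It does not show that those studies were adequately powered, or that this one is. A power statement for an indirect effect needs a treatment-to-mediator effect (a-path), a mediator-to-abstinence effect (b-path), an abstinence rate and the group sizes being compared. Section 9 gives only the last of these, and then argues from the total.

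The total is the wrong quantity for 2a and 2b, because the smallest group governs the precision of a contrast with UC. Aim II is one of two aims, and Section 9 will test mediation whether or not the treatment effect is significant. A reader who accepts the stated 80% could give a null mediation result more weight than the design supports.

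**Working it through.** **The plan's own figure.** The total reproduces: 3 × 145 + 50 = 485. The 80% for mediation can be neither reproduced nor refuted, because no mediation input is given.

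**Inputs from Section 9.** Two-sided 0.05; 20% attrition; 145 per active arm; 50 in UC. After attrition: 145 × 0.8 = 116, 50 × 0.8 = 40, and pooled 435 × 0.8 = 348.

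**Inputs assumed, because the documents give none.** a-path d = 0.33 to 0.35, borrowed from the abstinence effects, with 0.50 and 0.65 as larger cases; b-path odds ratio (OR) per mediator SD of 1.5, 2.0 and 2.5; 15% abstinence at the UC mediator mean; no direct effect.

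**Step 1: a-path, one measurement occasion.** With SE = √(1/n₁ + 1/n₀), power ≈ Φ(d/SE − 1.960), and the smallest d with 80% power is (1.960 + 0.842) × SE.

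| Contrast after attrition | SE | Power at d=0.33 | Power at d=0.35 | Smallest d for 80% |
|---|---|---|---|---|
| One arm v UC, 116 v 40 | 0.183 | 44% | 48% | 0.51 |
| Three arms v UC, 348 v 40 | 0.167 | 51% | 55% | 0.47 |
| 2c, 116 v 116 | 0.131 | 71% | 76% | 0.37 |

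For example, 116 v 40 at d=0.35: 0.35/0.183 = 1.91, and Φ(1.91 − 1.96) = 48%. With no attrition, power at d = 0.33 to 0.35 is 52-57% (145 v 50) and 60-65% (435 v 50).

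Why the total misleads: with 40 in UC and unlimited active participants, SE = √(1/40) = 0.158, so the smallest d is still 2.802 × 0.158 = 0.44.

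**Step 2: indirect effect.** When both paths must be significant, power cannot exceed that of the a-path. Simulation with a linear a-path and logistic b-path, 1,500 runs per cell (error about ±2.5 points):

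| Contrast | d | OR 1.5 | OR 2.0 | OR 2.5 |
|---|---|---|---|---|
| 116 v 40 | 0.35 | 21% | 42% | 49% |
| 116 v 40 | 0.50 | 33% | 69% | 78% |
| 116 v 40 | 0.65 | 43% | 86% | 94% |
| 348 v 40 | 0.35 | 47% | 57% | 57% |
| 348 v 40 | 0.50 | 72% | 86% | 84% |
| 116 v 116 (2c) | 0.35 | 46% | 77% | 78% |
| 116 v 116 (2c) | 0.50 | 59% | 95% | 96% |

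A repeat run agreed within simulation error, with 20% in the lowest cell. A Monte Carlo confidence interval, standing in for the planned bootstrap, came within 3 points in these cells.

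**Step 3: possible gain from repeated measures.** Assume a correlation of 0.5 between occasions, adjustment for the baseline mediator, and the mean of three follow-ups. The mean has variance (1 + 2 × 0.5)/3 = 0.667; baseline adjustment removes 0.5² = 0.25, leaving 0.417, so SE shrinks by √0.417 = 0.645. For 116 v 40 at d=0.35: 0.35/(0.183 × 0.645) = 2.96, giving 84% on the a-path. Joint power at d=0.35, for OR 1.5, 2.0 and 2.5, is then about 42%, 84% and 90% pooled, and 17%, 44% and 68% for one arm v UC. Without baseline adjustment, pooled a-path power is about 73%.

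**The case against.** A reader might infer that a UC arm of 50 cannot give 80% power for mediation. The documents do not support that:

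- They state no mediator effect, b-path or abstinence rate, so no figure can be called the trial's true power. The d of 0.33 to 0.35 describes abstinence; applying it to mediators is an assumption.
- Power passes 80% at larger effects, for example pooled d=0.50 with OR 2.0 (86%), or one arm with d=0.65 and OR 2.0 (86%).
- The planned analysis is multilevel mediation on repeated questionnaires and every-other-day diaries. Step 3 shows that the pooled contrast could reach 80% even at d=0.35 if the b-path is strong.
- Multiple imputation and off-site surveys are planned, so losing a full 20% of the information is a pessimistic case.
- The UC limit does not touch hypothesis 2c.

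All of this stands, and it limits the numbers to illustrations. It does not rescue the statement in Section 9. The repeated-measures gain is not claimed there, and the listed covariates are demographics and nicotine dependence, not the baseline mediator. As the Section 6.1 schedule reads in the public file, the withdrawal and social-support scales have no baseline entry. Averaging mediators over weeks 8, 12 and 24 would also overlap the outcome times and weaken temporal order. If the sponsor relies on this gain, the plan should say so and quantify it.

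**Conclusion.** The point holds as an unsupported claim, not as an arithmetical error. That the 80% has no calculation behind it, and that 485 is the wrong number for 2a and 2b, follows from the documents alone. The size of the shortfall depends on assumptions. At a mediator effect of d=0.35, measured once after attrition, power for the indirect effect is about 20-49% for one arm v UC and 47-57% pooled. The a-path alone needs d of 0.51 and 0.47 to reach 80%, and 0.37 for 2c. The simulations are single-level in Step 2, include none of the planned covariates and make no allowance for testing eight mechanisms.

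**What to change.** In the power paragraph of Section 9, delete the literature-count argument, the blanket 80% for mediation and the conclusion that 485 suffices for all aims. In their place, for each mediation contrast (each arm v UC, pooled arms v UC, MBAT + iQuit Mindfully v MBAT), give simulated power for the indirect effect or the smallest mediator effect detectable at 80%. Use the actual arm sizes and the planned repeated-measures model. State the a-path, b-path, abstinence rate, attrition, between-occasion correlation, any baseline-mediator adjustment and the number of mediators tested. Labelling the single-arm v UC mediation tests exploratory is optional.

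The cost is a short simulation, a rewritten paragraph and probably a less favourable stated figure. Enrolment and allocation do not change.

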10. DATA COLLECTION AND QUALITY ASSURANCE

During this study, psychosocial assessments and biochemical confirmation of smoking will be conducted at baseline and at regular intervals. All of the materials collected are for research purposes only, and data will be kept in strict confidence. Confidentiality will be ensured by use of identification codes. All data will be identified with a randomly generated identification code unique to the participant. The master list containing participant numbers and participants' names will be kept in a locked file, accessible to study staff only. Although participants will sign informed consent documents, these forms will be kept in a separate locked file and will never be connected to the study data. No names will ever be recorded on the questionnaires, which will be stored in a locked file cabinet and available only to the research personnel.

The online screener will be conducted using the GSU-hosted Qualtrics platform. The qualtrics^{xm} Security Statement (January 31, 2020) reads: "Qualtrics' most important concern is the protection and reliability of customer data. Our servers are protected by high-end firewall systems and scans are performed regularly to ensure that any vulnerabilities are quickly found and patched. Application penetration tests are performed annually by an independent third-party. All services have quick failover points and redundant hardware, with backups performed daily. Access to systems is restricted to specific individuals who have a need-to-know such information and who are bound by confidentiality obligations. Access is monitored and audited for compliance. Qualtrics uses Transport Layer Security (TLS) encryption (also known as HTTPS) for all transmitted data. Surveys may be protected with passwords. Our services are hosted by trusted data centers that are independently audited using the industry standard SSAE-18 method."

Questionnaire data will be collected using the REDCap (Research Electronic Data Capture) system available at Georgia State University. This will provide a secure way to collect and manage data, while avoiding potential issues with manual data entry. Georgia State University belongs to a consortium of institutional partners that work to maintain a software toolset and workflow methodology for electronic collection and management of research data. REDCap data collection projects rely on a study-specific data dictionary defined by the research team. REDCap also contains a Survey tool for building and managing online surveys. The research team can create and design surveys in a web browser and engage potential respondents using a variety of notification methods. Both REDCap and REDCap Survey systems provide secure, web-based applications that are flexible enough to be used for a variety of types of research, provide an intuitive interface for users to enter data and have real time validation rules (with automated data type and range checks) at the time of entry. These systems offer easy data manipulation with audit trails and reporting for monitoring, reporting, and querying patient records, and an automated export mechanism to common statistical packages (SPSS, SAS, Stata, R/S-Plus). REDCap application is securely housed in Amazon AWS and managed by the Research Solutions department at Georgia State University. All web-based information transmission is encrypted and the data is encrypted at rest. Amazon AWS's data centers are state of the art nondescript and secured facilities. Data will be downloaded from REDCap into a secure server that is managed by Georgia State University, password-protected, and available only to research personnel who have completed training in research with human subjects.

Additional safeguards will include appropriate password protection and physical security for all computer systems and physical data. Personal names will not be stored in electronic data files. Physical data will be stored in a locked file cabinet and available only to the research personnel. The master list containing participant numbers and participants' names will be kept in a separate locked file, also accessible to study staff only.

The Mobile Commons platform maintains a high level of security control for sending and receiving text messages. The Mobile Commons HIPAA and Text Messaging Security White Paper indicates: "All

Mobile Commons systems that transmit or store sensitive client information are housed in a secure data center facility that maintains a high standard of physical security controls.... The Mobile Commons information security program includes comprehensive technical security measures geared towards protecting the confidentiality, integrity, and availability of sensitive client data.... Authentication controls are in place for access to all systems and applications that deal with sensitive client data. All activity regarding access to, and transmission of, this data is logged. Sessions are configured to timeout after a period of inactivity. All sensitive data, including PHI and authentication credentials for system and application access, are transmitted via encrypted protocols (SSL or SSHv2) when traversing public or untrusted networks. Strong encryption is used for sensitive data stored on Mobile Commons systems. Multiple layers of procedures and technical controls are in place to verify the identity of any person or entity seeking access to any sensitive client information" (https://www.mobilecommons.com/wp/wp-content/uploads/2014/07/Mobile-Commons-HIPAA-Text-Messaging-Security-White-Paper1.pdf).

